## **Efficacy**

- Change from baseline to Weeks 8, 12, 16, 20, and 39 in C-peptide  $AUC_{0-2h}$  and change from baseline to Week 52 in C-peptide  $AUC_{0-4h}$  following an MMTT.
- Change from baseline to Weeks 16, 20, 26, 39 and 52 in average daily insulin dose.
- Time to onset of biological response of C-peptide following MMTT.
- Percent of subjects achieving a positive stimulated C-peptide (defined as > 0.2 ng/mL) after implant
- Percent of subjects who achieve a 50% reduction in average weekly exogenous insulin dose from baseline to Weeks 16, 20, 26, 39, and 52.
- Percent of subjects who achieve exogenous insulin independence; of those subjects achieving insulin independence, the percent achieving HbA1c < 7.0%.

- Percent of time spent with blood glucose values at various cut points (e.g., <54 mg/dL, ≥54 to < 70 mg/dL, ≥70 mg/dL to ≤180 mg/dL, >180 mg/dL and >250 mg/dL) as measured by each subject's CGM.
- Change from baseline to Weeks 16, 20, 26, 39 and 52 in time-in-euglycemic range (≥70 mg/dL to ≤180 mg/dL), time-in-hypoglycemic ranges (<54 mg/dL and ≥54 to <70 mg/dL), and time-in-hyperglycemic ranges (>180 mg/dL and >250 mg/dL) as measured by each subject's CGM.
- Change from baseline to Weeks 16, 20, 26, 39, and 52 in weekly frequency of hypoglycemic events;
- Change from baseline in frequency of hypoglycemic events (24-hour; daytime [start between 6a.m.-12a.m.]; nocturnal [start between 12a.m.-6a.m.]) to Weeks 16, 20, 26, 39 and 52.
- Percent of subjects free of severe hypoglycemic events between study visits starting with Week 16 (i.e., Weeks 16-20, Weeks 20-26, Weeks 26-39, Weeks 39-52/ET, and Weeks 16-52/ET).

## **Exploratory Endpoint:**

• Histological results of explanted units and any associated tissue capsule as evaluated for cell viability, vascularization, immune response, and/or cell maturation and differentiation.

## 5 Analysis Plan Overview

No decision-making interim analyses (e.g., for early stopping for efficacy or futility, or for modification to the planned enrollment) are planned. A descriptive analysis may be produced when all subjects in Cohort 2 have reached their Week 26 visit to support regulatory discussions. This report, if produced, will summarize key safety and efficacy endpoints for those subjects.

To help assess specific safety events in this early phase study and/or to evaluate the implantation and explantation techniques, the Sponsor or designee, Medical Monitor, and site Surgeon(s) and/or Investigator(s) will maintain close communication. There will be an independent Data Safety Monitoring Board (DSMB) available.

The final summarization of the data will be performed after official database lock, once the last subject in Cohort 2 has completed his/her Week 53/Follow-up visit.

The phrase "treatment group" is used in this section to denote the number of initially implanted sentinel units in Cohort 1 or initially implanted VC-01-DF units in Cohort 2. In Cohort 1, if a subject has a sentinel unit explanted for any reason and remains in the study, then he/she will be included in the treatment group that is described by the number of sentinel units originally implanted. For Cohort 2, if a subject has a VC-01-DF unit explanted for any reason and remains in the study, then she/he will be included in the treatment group that is described by the number of VC-01-DF units originally implanted. If no VC-01-DF units are implanted into a Cohort 2 subject, but sentinel units are implanted, then the subject will be included in the "0 implanted VC-01-DF units" treatment group. If, during the course of the study, further enumeration is needed to

differentiate treatment group (for example, if it is necessary to differentiate multiple EDDS configurations used in Cohort 1), then that further detail will be included in this study SAP (that is, this SAP will be amended to include that information).

Where appropriate, data from subjects in Cohort 1 and in Cohort 2 will be summarized together (within the same table). When data from the two cohorts is included in the same table, the treatment group will be used to differentiate the data from Cohort 1 and Cohort 2.

All data that are collected in the study will be provided in a listing. In general, listings will be sorted by Cohort, then treatment group, investigative site and subject number, and, where appropriate, study visit/start date.

## 6 Analysis Sets

## 6.1 Full Analysis Set

The Full Analysis Set (FAS) is defined as all subjects who were enrolled into the study and received implantation of at least one sentinel and/or VC-01-DF dose-finding unit on Study Day 1/Visit 3. The FAS will be used for all efficacy summaries/analyses and listings.

## 6.2 Safety Analysis Set

The Safety Analysis Set (SAS) is defined as all subjects who were enrolled into the study and in whom an implant surgery was attempted, regardless if any sentinel or dose-finding units were actually implanted. The SAS will be used for safety summaries and listings.

## 7 Statistical Analyses

[figure not shown]
## 7.1 Statistical Power and Sample Size Considerations

There are no statistical hypotheses being tested.

In Cohort 1, up to 30 subjects will be enrolled. In Cohort 2, up to 40 subjects will be enrolled, for a total enrollment of up to 70 subjects in both cohorts.

The sample size in Cohort 1 was empirically derived, based upon safety considerations and data accumulated from other previously performed ViaCyte clinical trials. A sample size of up to 30 subjects should allow for adequate assessment of Cohort 1 study objectives.

A sample size of 40 subjects in Cohort 2	
u u	
	Since Cohort 1 has the primary objective of
evaluating initial safety and tolerability, the	ese subjects will not contribute MMTT data
for the Week 26 analysis.	

For the 2-hour MMTT, a sample size of 40 subjects will

## 7.2 Baseline, Endpoint and Missing Value Definitions

#### 7.2.1 Baseline

Baseline will be defined as the last non-missing value prior to the start time of the surgical implantation procedure unless otherwise specified. For MMTTs in Cohort 2 subjects, the 4-hour MMTT performed during the Screening period is used for defining both the baseline 4-hour MMTT and the baseline 2-hour (using the first 2 hours of data) MMTT.

## 7.2.2 Analysis Visit Windows

For the purpose of analyzing time to event endpoints, the time-in-study for each subject will be measured relative to Day 1, the day that the surgical implantation procedure was attempted.

The data will be summarized based on the electronic case report form (eCRF) (Study Visit) in which it was collected as long as the data are within the windows specified. If data for a particular Study Visit is not within the windows specified, then queries will be sent to the site to confirm data entry. Data collected as an unscheduled visit will be reassigned to a Study Visit based on the SAP visit windows specified.

Because subjects are not always able to complete visits on the scheduled target day, visit windows will be used for associating data with specific time points. The visit windows are given below.

#### Cohort 1:

In Cohort 1, the Screening Period for each subject is expected to be approximately two (2) weeks in duration and comprised of two (2) study visits. Subjects qualifying for entry into Cohort 1 and who subsequently are implanted with VC-01 sentinel units may complete an additional ten (10) study visits over a period of approximately six (6) months. It is expected that a subject who completes the planned entire duration of the trial will therefore have a total of 12 study visits spanning approximately seven (7) months (including Screening, Treatment Period, and final Follow-up Visit). If the Sponsor has planned/scheduled an earlier explant (for non-safety reasons), this subject will also be considered as completing the study early (ET) with fewer study visits, as applicable.

Cohort 1 Visit Windows

Visit Label	Target Day	Window for Summarization				
V1 Screen (Week -2)	-14	≤-11				
V2 Screen (Week -1)	-7	[-10, -1]				
V3 Enroll (Day 1)	1	[1]				
V4 (Day 2)	2	[2, 8]				
V5 (Week 2)	15	[9, 22]				
V6 (Week 4)	29	[23, 43]				
V7 (Week 8)	57	[44, 71]				
V8 (Week 12)	85	[72, 99]				
V9 (Week 16)	113	[100, 127]				
V10 (Week 20)	141	[128, 162]				
V11 (Week 26)	183	[163, 186]				
V12 (Week 27/Follow-up)	190	≥187				

#### Cohort 2:

In Cohort 2, the Screening Period for each subject is expected to be approximately five (5) weeks in duration and comprised of two (2) study visits. Subjects qualifying for entry into Cohort 2 and who subsequently are implanted with VC-01 sentinel units and/or dose-finding units (VC-01-DF) may complete an additional 12 visits over a period of approximately one (1) year. It is expected that a subject who completes the planned entire duration of the trial will therefore have a total of 14 study visits spanning approximately 13 ½ months (including Screening, Treatment Period, and final Follow-up Visit). If the Sponsor has planned/scheduled an earlier explant (for non-safety reasons), this subject will also be considered as completing the study early (ET) with fewer study visits, as applicable.

Cohort 2 Visit Windows

Conort 2 Visit Windows	ı	I
Visit Label	Target Day	Window for
		Summarization
V1 Screen (Week -5)	-35	≤ - 32
V2 Screen (Week -4)	-28	[-31, -1]
V3 Enroll (Day 1)	1	[1]
V4 (Day 2)	2	[2, 8]
V5 (Week 2)	15	[9, 22]
V6 (Week 4)	29	[23, 43]
V7 (Week 8)	57	[44, 71]
V8 (Week 12)	85	[72, 99]
V9 (Week 16)	113	[100, 127]
V10 (Week 20)	141	[128, 162]
V11 (Week 26)	183	[163, 228]
V12 (Week 39)	274	[229, 319]

V13 (Week 52)	365	[320, 368]
V14 (Week 53/Follow-	372	≥ 369
up)		

## 7.2.3 Replicate Data

For data summarization and/or analysis for each parameter, if multiple study visits (including unplanned visits) occur within the same visit window, then precedence will be given to the study visit at which an MMTT was performed. If no MMTT was performed at either visit, then if there is a study visit and an unplanned visit within the same window, then the data from the study visit will be used. Otherwise, the study visit on the day that is closest to the target day will be used, as long as there are data for that parameter. All data from all study visits (planned, unplanned, and replicate)will be provided in the data listings.

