6.15. Unplanned/Unscheduled Visits

Unplanned visits may occur at any time for reasons of subject safety and/or collection of additional time-point data. Possible reasons for unplanned visits include but are not limited to:

• Adverse event follow-up.

- Abnormal laboratory test follow-up.
- Additional pre-operative evaluations.
- Post-implant and/or explant site evaluation (includes evaluation of incision healing).
- Suture removal post-procedure.
- Repeat or follow-up ultrasound evaluations (safety or location).
- Explant of a VC-01 unit.
- Obtain video and/or photos of an explantation procedure.
- Review of blood sugar values with possible exogenous insulin dose adjustments.
- Perform an SOGCT or MMTT.

Source documentation should reflect the occurrence of all Unplanned Visits. Data may be collected from these visits depending on the procedures conducted. A subject may need to be in a fasted state for Unplanned Visits depending on the laboratory tests required (e.g., lipid panel).

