7.17.1. Routine Clinical Laboratory Evaluations

Subjects will have routine laboratory assessments performed throughout the study, including:

- Hematology: Hemoglobin, hematocrit, red blood cell (RBC) count, platelet count, white blood cell (WBC) count, neutrophils (total), eosinophils, monocytes, basophils, and lymphocytes.
- Chemistry: Blood urea nitrogen (BUN), serum creatinine, total calcium, sodium, potassium, chloride, bicarbonate, magnesium, phosphate, uric acid, ALT, AST, LDH,

alkaline phosphatase, total bilirubin (direct and indirect bilirubin reflexively measured only when total bilirubin is greater than the ULN), creatine phosphokinase, albumin, and total protein.

If a subject demonstrates an ALT and/or AST values of >3 x ULN during the study, the subject will re-test every five to seven days until the values return to <3 x ULN. An ALT or AST value of >3 x ULN with total bilirubin ≥ 2 x ULN and alkaline phosphatase <2 x ULN will require re-testing every three to five days.

- Fasting serum lipid panel: Total cholesterol, high density lipoprotein (HDL)-C, calculated low-density lipoprotein (LDL)-C, triglycerides, very low-density lipoprotein (VLDL). Non-HDL-C will be calculated as TC HDL-C. When triglycerides are >400 mg/dL, another sample will need to be collected from the subject and a directly measured LDL will be done.
- Urinalysis (lab dipstick): pH, protein, blood, ketones, leukocyte esterase, and nitrites.
 Microscopy is done if the dipstick sample is positive for blood, nitrites, leukocytes, and/or
 protein. A bacterial culture and sensitivity will be done if nitrites or leukocyte esterase are
 positive. Another sample will need to be collected from the subject and submitted in order
 to perform the culture and sensitivity testing.

At visits where a urine albumin/creatinine ratio is performed, the determination must be made on the first morning void.

- Serology: screening for hepatitis B core and surface Ag/Ab, hepatitis C virus, and HIV (1&2).
- Other:
 - Cohort 1: HbA1C, urine pregnancy tests, Quantiferon, renal function evaluation via eGFR calculation, and thyroid stimulating hormone (screening). Drug screen at Visit 1 only.

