## 7.3.7.2 Cohort 2 Secondary Safety Analyses

Unless otherwise specified, the SAS will be used for the safety summarizations for the Cohort 2 subjects. Adverse events and SAEs will be summarized by system organ class (SOC), by severity, and by relationship. This will be done by treatment group and overall. As with the Cohort 1 subjects, the summarization of AEs for Cohort 2 will focus on only those events that are TEAEs, but the AE listings will include all reported AEs regardless of when they started.

Other safety data, such as vital signs, clinical laboratory data, and hypoglycemic events will be summarized by study visit and treatment group, for the Cohort 2 subjects. Change from baseline in safety data will also be summarized in a similar manner. Physical examination data will be listed by subject.

The number of Cohort 2 subjects experiencing off-target growth as evidenced by implanted VC-01 units via lumen ultrasound (lumen thickness > 1 mm) measurements, or by histological examination of explants will be summarized by treatment group.

For immune response as measured by serum immunoglobulin and hematological assays, any Cohort 2 subject who appears to be having an immune response will have all relevant data described in a clinical narrative. In addition, data of interest from the assays may be summarized by treatment group and overall. For the incidence of immune sensitization, a listing will be provided for all subjects with a suspected event (the presence of donor anti-HLA antibodies absent prior to implant), with a column in the listing that indicates whether it is a confirmed immune sensitization (either confirmatory histological observations from at least one explanted unit and/or the presence of clinical symptoms; will have a corresponding 'sensitization' AE).

Implantation site assessments will be summarized at each time-point post-implantation and each visit thereafter. For each site assessment symptom, the number of Cohort 2 subjects with the symptom at that time-point will be summarized by treatment group and overall.

Finally, the number of Cohort 2 subjects undergoing a premature VC-01 unit explant will be provided in a listing (separate from the overall explant listing), which includes the reason for explantation (i.e., safety issue, malfunction, damaged, planned explant, etc.).

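### SAP 7.2.3 applies its one-value-per-window rule to safety data, so a worse laboratory or vital-sign value first found at an unplanned visit is usually left out of the by-visit tables, and no worst-value table recovers it

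*SAP*

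**What the plan says.** SAP 7.2.2 places unplanned data in the visit windows: "Data collected as an unscheduled visit will be reassigned to a Study Visit based on the SAP visit windows specified".

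SAP 7.2.3 then chooses among values that share a window. Its scope is general: "For data summarization and/or analysis for each parameter, if multiple study visits (including unplanned visits) occur within the same visit window". The first criterion is that "precedence will be given to the study visit at which an MMTT was performed". If neither visit had an MMTT, "if there is a study visit and an unplanned visit within the same window, then the data from the study visit will be used". Values not chosen are kept for review: "All data from all study visits (planned, unplanned, and replicate)will be provided in the data listings".

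The one place where the SAP handles safety data differently is 7.2.6.7, which leaves early-termination safety data unmapped. It does not mention unplanned visits.

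For Cohort 2, SAP 7.3.7.2 states: "Other safety data, such as vital signs, clinical laboratory data, and hypoglycemic events will be summarized by study visit and treatment group". SAP 7.3.7.1 does the same for Cohort 1 laboratory and vital-sign data. Change from baseline is tabulated in the same by-visit way. Neither section plans a worst post-implant value, a shift table or an any-time abnormality count for these data.

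The protocol foresees unplanned tests. Section 6.15 lists follow-up of abnormal laboratory results among the reasons for an unplanned visit. Section 7.17.1 requires that after ALT or AST above three times the upper limit "the subject will re-test every five to seven days until the values return to <3 x ULN", with a shorter interval when bilirubin is also raised.

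**The concern.** Choosing one value per window is sensible for a table of means by visit. It suits safety less well, where the question is often how far a parameter moved in any subject at any time. Here the by-visit tables are the only planned summaries of laboratory and vital-sign data. A subject could have an unremarkable scheduled result and a markedly abnormal unplanned result some weeks later in the same window, and the tables would show only the first.

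The leading criterion, whether an MMTT was done, is an efficacy consideration. In Cohort 2 it will often decide which chemistry result is tabulated. At stake is whether the summaries by treatment group (number of units implanted) show the extreme values that were recorded. Safety and tolerability is a secondary objective in both cohorts.

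**Working it through.** The plan gives no figure to reproduce. The check is how often an unplanned value shares a window with a scheduled value of the same parameter.

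**Inputs.** Window limits come from SAP 7.2.2. Scheduled tests come from the schedules of assessments (Protocol Tables 1 and 2; SAP section 8). Length = last day − first day + 1.

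| Window | Days | Length | Hematology/chemistry | Safety ultrasound | MMTT (Cohort 2) |
|---|---|---|---|---|---|
| V3 | 1 | 1 | yes | no | no |
| V4 | 2–8 | 7 | no | no | no |
| V5 | 9–22 | 14 | yes | no | no |
| V6 | 23–43 | 21 | yes | no | no |
| V7 | 44–71 | 28 | yes | yes | yes |
| V8 | 72–99 | 28 | yes | no | yes |
| V9 | 100–127 | 28 | yes | yes | yes |
| V10 | 128–162 | 35 | yes | no | yes |
| V11, Cohort 1 | 163–186 | 24 | yes | yes | – |
| V11, Cohort 2 | 163–228 | 66 | yes | yes | yes |
| V12, Cohort 2 | 229–319 | 91 | yes | no | yes |
| V13, Cohort 2 | 320–368 | 49 | yes | yes | yes |

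The windows have no gaps: Days 1–186 in Cohort 1 and Days 1–368 in Cohort 2, before the open-ended follow-up window.

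**Hematology and chemistry.** Only V4 lacks a scheduled sample.
- Cohort 1: 186 − 7 = 179; 179/186 = 96.2%.
- Cohort 2: 368 − 7 = 361; 361/368 = 98.1%.
- Leaving out Day 1, whose sample belongs to the pre-implant work-up: 178/185 = 96.2% and 360/367 = 98.1%.

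**Vital signs.** These are scheduled at every visit, so every window has a scheduled value.

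**Which sentence decides in Cohort 2.** Windows V7 to V13 each have a scheduled MMTT: 28 + 28 + 28 + 35 + 66 + 91 + 49 = 325; 325/368 = 88.3%. There the MMTT sentence normally applies before the scheduled-over-unplanned sentence. The scheduled visit still usually wins, because that is where the MMTT is done.

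**Ultrasound, for comparison.**
- Cohort 1: 28 + 28 + 24 = 80; 80/186 = 43.0%.
- Cohort 2: 28 + 28 + 66 + 49 = 171; 171/368 = 46.5%.

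**Illustration (assumed dates).** A Cohort 2 subject has the scheduled Week 26 sample and MMTT on Day 183, with normal ALT. An unplanned sample on Day 205 is clearly abnormal. Both days fall in 163–228, so the Week 26 tables show only Day 183. If ALT is normal again at the Week 39 sample (target Day 274), no laboratory table shows the rise.

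**The case against.** The strongest reply is that a by-visit table needs one value per window and that preferring the scheduled value is a reasonable, pre-specified choice. Nothing is lost from the record, because every value is listed. An abnormal result that causes symptoms, needs further diagnostic work or intervention, or is judged to be an AE by the investigator or sponsor is reported as one (Protocol 8.1.3) and enters the AE tables. With at most 70 open-label subjects, listings can be read subject by subject. Most of this stands, and it limits the point to the laboratory and vital-sign tables. It does not remove it: listings give no rate by treatment group, AE status is partly a judgement, and AE tables do not show the size of a laboratory change.

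Three stronger readings are tempting, and the documents do not support them.

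- *The rule biases safety data toward normal in general.* It does not. If the scheduled value was the abnormal one, the rule keeps it and leaves out the later, resolving re-tests. Section 7.17.1 re-testing follows a value already above three times the upper limit, so where that value was scheduled the table shows it. The loss arises only when the worse value first appears at an unplanned visit. Protocol 6.15 also lists many reasons for such visits that have nothing to do with an abnormal finding.
- *A lumen reading above 1 mm at an unplanned scan is discarded.* Off-target growth is a count of subjects by treatment group, not by visit, and its natural reading is any scan. It can also be met through histology. The general wording of 7.2.3 leaves this unclear, but the SAP does not say such a scan is dropped. On more than half of the window days there is no scheduled scan to compete with it.
- *New donor anti-HLA antibodies could be overridden in the same way.* SAP 7.3.7.1 and 7.3.7.2 already promise a listing of all suspected cases with confirmed ones marked, so no problem is shown there.

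**Conclusion.** The point holds for laboratory and vital-sign summaries. As written, a worse value first found at an unplanned visit is left out of those tables whenever a scheduled value falls in the same window. For hematology and chemistry, such windows make up about 96% of Cohort 1 and 98% of Cohort 2 window days.

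Those percentages are shares of calendar days. They assume that the scheduled sample was taken and the subject was still in the study, and they do not estimate how many values will be displaced, since the documents give no rate of unplanned tests. Two exceptions apply: an unplanned visit that includes an MMTT takes precedence over a scheduled visit without one, and an unplanned value with no scheduled value in its window has no competitor.

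This is a worthwhile, inexpensive improvement to the safety reporting. It affects neither the primary efficacy analysis nor the conduct of the trial.

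**What to change.** Three changes to the SAP:

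1. In 7.2.3, state that the rule applies to efficacy analyses and to by-visit summary tables only.
2. In 7.3.7.1 and 7.3.7.2, add one table of shift from baseline to worst post-implant value for hematology, chemistry and vital signs. It should use all scheduled and unplanned values, be shown by treatment group and overall, and define the direction of worst for each parameter.
3. As a clarification, state that the off-target-growth count (lumen thickness above 1 mm) uses every planned and unplanned scan.

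The cost is a few sentences and one standard table from data already collected. The downside is that subjects tested more often have more chances to show an extreme value; a footnote with the number of tests in each treatment group lets the reader allow for that.
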